Statistical Methodology	
Pilot:
 
 Sensitivity and specificity will be calculated along with exact 95% confidence intervals (CIs). Sensitivity will be calculated as the proportion of patients with toxicity captured by the text-based e-triage among patients with toxicity as documented by the provider in the EMR. Specificity will be calculated as the proportion of negative e-triage screens among patients without symptoms as documented by the provider in the EMR. 
Randomized control trial:
 
 The primary analyses will be Intent-to-Treat, with the primary outcome (total care time measured over three months) compared using a two-sample t test, or Wilcoxon test if normal distribution assumption is violated. A multivariate linear regression model will adjust for potential confounders. As a secondary analysis, “as treated” analyses will be performed to account for permissive non-adherence to the triage assignment. Standard descriptive statistics will be used to describe patient factors associated with more frequent triage non-adherence. Secondary endpoints include: total wait time measured over three months or at least 3 office visits, total number of hospitalization/emergency department encounters, patient satisfaction [The Patient Satisfaction Questionnaire Short Form (PSQ-18)]¹, provider satisfaction (Net-Promoter Score)^{2,3}, and health related quality of life [Functional Assessment of Cancer Therapy-General (FACT-G)⁴]. Total wait time and number of hospitalizations will be compared between groups using Wilcoxon rank sum test. The rest of the secondary endpoints will be measured at multiple time points and longitudinal linear mixed-effects model will be used to compare the group difference over time.
Data and Safety Monitoring Plan	
Trial oversight will be conducted by the University of Pennsylvania Institutional Review Board. Safety will be monitored on an ongoing basis by the PI, study team, and institutional experts not involved in the study.

CONFIDENTIAL

Background and Study Rationale

This study will be conducted in full accordance with all applicable University of Pennsylvania Research Policies and Procedures and all applicable Federal and state laws and regulations including the following regulations as they apply: 45 CFR 46, 21 CFR Part 50. All episodes of noncompliance will be documented.

1 Introduction

1.1 *Background and Relevant Literature*

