6.1 Sample Size and Power Determination

AIM 1 Pilot study: This protocol describes a cross-sectional study designed to investigate the operating characteristics of a text-based e-triage to capture patients experiencing immune-related adverse events against the gold standard of documented toxicity assessments in the EMR. Due to the granular nature of our e-triage questionnaire we believe a sensitivity of 95-100% is very reasonable to anticipate.

Results from the interim analysis including 48 patients are shown in Table 1. Median age was 68.5 (IQR 58-72), 58% were female, 88% white, and most patients either had thoracic (25%), genitourinary (27%), head/neck (15%), or skin (15%) cancers. 53.2% of patients had at least 1 toxicity related adverse event documented in the EMR. Sensitivity to identify at least one toxicity related adverse event was 100% (95% CI 0.863-1.00) aligning with our primary endpoint. Despite being at our target sensitivity we identified two underperforming questions (pain and rash) and therefore optimized the instrument creating a version 2 (see appendix). Assuming the sensitivity and prevalence are same as those in the preliminary data, a sample of 47 patients will produce adequate precision for the estimate for sensitivity, with the half width of the 95% confidence interval no larger than 7%.

AIM 2 Randomized control trial: We plan to enroll 176 patients and expect to have 160 patients left assuming a 10% drop out rate (e.g., due to disease progression and need to change therapy). Based on the preliminary data recently published by this group measuring total care time of patients treated at the Penn Abramson Cancer Center⁸, we expect the total care time in the control group to have a mean of 130 hours with a SD of 118. A sample size of 80 per group will provide 79% power to detect a 40% reduction in the total care time (130 vs. 78) assuming a type I error rate of 0.05.

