6.2 Statistical Methods

Aim 1 Pilot study: Sensitivity and specificity will be calculated along with exact 95% confidence intervals (CIs). Sensitivity will be calculated as the proportion of patients with toxicity captured by the text-based e-triage among patients with toxicity as documented by the provider in the EMR. Specificity will be calculated as the proportion of negative e-triage screens among patients without symptoms as documented by the provider in the EMR. We will additionally be performing a series of psychometric analyses including response distribution to assure responses are not skewed, item-scale correlation, internal consistency, floor and ceiling effects and item reduction as well as response rates.

Table 2. Power to detect reduction in total care time (N=160)	
Reduction in care time	Power
35%	68%
40%	79%
45%	88%
50%	93%

AIM 2 Randomized control study: Standard descriptive statistics will be calculated to compare patient characteristics for the intervention arm versus the control arm, such as medians and interquartile ranges for continuous variables and frequencies and proportions for categorical variables. These characteristics will be compared between the two groups using the Wilcoxon rank sum test for continuous variables and the chi squared or Fisher's exact test for categorical variables. We expect these characteristics will be similarly distributed between the intervention groups due to randomization, but in the case of imbalance, they may be adjusted in the multivariable model of the outcome.

The primary analyses will be Intent-to-Treat, with the primary outcome (total care time) compared using a

CONFIDENTIAL

two-sample t test, or Wilcoxon test if normal distribution assumption is violated. A multivariate linear regression will be used to adjust potential confounders including demographics (age, gender, race, SES), comorbidities (Elixhauser comorbidity index), treatment intent (curative versus palliative), and performance status. The final model will be established using stepwise forward regression based on 10% change in effect estimate for intervention. As a secondary analysis, “as treated” analyses will be performed to account for permissive non-adherence to the triage assignment. Standard descriptive statistics will be used to describe patient factors associated with more frequent triage non-adherence.

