6.3 Control of Bias and Confounding

Patients will be randomized 1:1 to control or intervention arm of the study. Despite the benefits of randomization to minimize the risks of confounding we will additionally perform a multivariate linear regression to adjust potential confounders including demographics as describe in section 6.2.

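### The supporting adjusted model picks its covariates by how far they move the treatment estimate; fix the seven named covariates in advance instead

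*Protocol*

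**What the plan says.** The primary comparison of total care time is an unadjusted intent-to-treat t test, or a Wilcoxon test if normality fails (Protocol 6.2 and 6.3.2; SAP 1.2 and 1.3.2). A linear regression is added in support. Protocol 6.2 says that it adjusts for "potential confounders including demographics (age, gender, race, SES), comorbidities (Elixhauser comorbidity index), treatment intent (curative versus palliative), and performance status". That names seven covariates, but the list is introduced as examples and is not closed.

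The covariates that stay are decided as follows: "The final model will be established using stepwise forward regression based on 10% change in effect estimate for intervention". SAP 1.2 repeats this word for word. A second route into the model is optional: "in the case of imbalance, they may be adjusted in the multivariable model of the outcome". It appears in Protocol 6.2 and 6.3.1 and in SAP 1.2 and 1.3.1, with no definition of imbalance.

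Neither document gives an order of entry, the reference model for the 10% change, or a rule for an estimate close to zero.

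**The concern.** Change-in-estimate selection is a tool for finding confounders in non-randomized data. Under 1:1 randomization a covariate moves the arm estimate mainly through chance imbalance, so the rule does not pick covariates for their prognostic value. Because the bar is a share of the estimate itself, a small observed effect lets in almost anything and a large one lets in little.

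The adjusted model is there to show whether the primary result survives adjustment. It does this less convincingly when the same outcome data choose the adjustment, and a reader cannot know beforehand what will be in the model. Only the credibility and precision of a supporting estimate are at stake.

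**Working it through.** **Inputs from the documents (Protocol 6.1, SAP 1.1).** 80 per arm; control mean 130 h; SD 118 h; planned difference 130 − 78 = 52 h; alpha 0.05. **Assumed:** the share of care-time variance that the covariates explain (R²), which no document gives.

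**1. The plan's power.** SE = 118 × √(2/80) = 18.66 h, and 52/18.66 = 2.787. The two-sided noncentral t with 158 df gives 79.1%, against the stated 79%. The four rows of Table 2 also reproduce (67.9, 79.1, 87.6 and 93.3%, against 68, 79, 88 and 93%).

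**2. The bar.** 10% of 52 h is 5.2 h; 10% of 5 h is 0.5 h.

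**3. Chance of entry for one covariate.** If it explains a share r of the variance, chance imbalance shifts the arm estimate with SD √r × 118 × √(4/160).

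| r (assumed) | SD of shift | Entry if estimate is 52 h | Entry if estimate is 5 h |
|---|---|---|---|
| 0.10 | 0.316 × 118 × 0.158 = 5.9 h | P(\|Z\| > 5.2/5.9) = 38% | P(\|Z\| > 0.5/5.9) = 93% |
| 0.05 | 4.2 h | 21% | 90% |

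**4. The whole rule, by simulation.** 160 patients, normal errors, seven independent one-column covariates, 4,000 trials per setting. The rule is read as: add the covariate with the largest relative change, and stop when none reaches 10%.

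- R² = 0.2: about 4.5 covariates enter under no effect (4.2 to 4.6 across runs). About 1.2 enter at 52 h (1.0 to 1.2), where about 40% of trials admit none.
- R² = 0 and no effect: 2.2 useless covariates enter on average, and 77% of trials admit at least one.
- Entry order, in a separate run under no effect that tried 20 random orders per trial: more than one final model arose in 76% of trials at R² = 0.1 and in 92% at R² = 0.3.

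**5. Error rate and power.** Type I error under the rule was 2.7% to 5.7% across runs. Power at 52 h with seven columns:

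| R² (assumed) | 10% rule | All seven fixed |
|---|---|---|
| 0 | 79.0% | 77.3% |
| 0.05 | 79.5–80.1% | 79.4–79.7% |
| 0.1 | 81.0–81.3% | 82.1–82.4% |
| 0.2 | 81.5–83.3% | 84.4–85.7% |
| 0.3 | 86.5–86.9% | 90.2–90.6% |

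**6. Difference in what is reported.** At 52 h and R² of 0.1 to 0.3, the two adjusted estimates differ by a median of 3.0 to 3.7 h (90th percentile 8 to 11 h). They disagree on significance in about 4 to 7% of trials.

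**7. Price of the fixed model if the covariates predict nothing.** With k columns the variance grows by about 157/(157 − k), with 158 − k df.

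- k = 7: 157/150 = 1.047; noncentrality 2.787/√1.047 = 2.72; power 77.2%.
- k = 12 (race and SES in four levels, performance status in three): 157/145 = 1.083; noncentrality 2.68; power about 76%.

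The fixed model regains the unadjusted 79.1% at an R² of about 0.045 (7 columns) or 0.077 (12 columns). Against the 10% rule it gains above roughly 0.05 with 7 columns. With 12 columns it still trails by 0.3 to 0.5 points at 0.1 and leads by 1.4 to 2.0 points at 0.2.

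**The case against.** The best defence is that little depends on this model. The primary test is unadjusted, the regression is additional, and no confirmatory conclusion changes. That stands and sets the priority. It is also true that no document shows that the seven covariates predict care time. The endpoint includes commuting, and none of the seven measures it directly. The power case for a fixed list is therefore conditional, and the argument rests on pre-specification. The simulated rule is one reading of an incomplete description, so the percentages illustrate a pattern and do not forecast this trial.

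Four stronger readings are tempting and are not supported:

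- **Inflated type I error.** Applied mechanically, the rule stays near 5% and becomes conservative as R² rises. Taking the smallest p-value over 20 entry orders still gave only 5.3% and 4.7% rejection (R² = 0.1 and 0.3).
- **Falsely precise standard errors.** With seven columns the reported SE ranged from 3% too small to 10% too large, so the larger error is conservative.
- **A contradiction within the protocol.** The synopsis says "A multivariate linear regression model will adjust for potential confounders" and section 6.3 says "we will additionally perform a multivariate linear regression to adjust potential confounders", yet the rule can end with no covariate. But section 6.3 refers to 6.2 for the method. Under a change-in-estimate definition, a variable that does not move the estimate is not a confounder. An empty model is then the rule's own answer.
- **Failure under unequal dropout.** The plan does "expect to have 160 patients left assuming a 10% drop out rate", but gives no difference by arm. In a simulation at R² = 0.1 with a true effect of 52 h, one covariate was shifted by 0.3 SD between arms. The mean estimates were 48.0 h crude, 51.5 h under the rule and 52.4 h fixed. With a 0.5 SD shift they were 44.9, 51.3 and 51.9 h. The rule recovers nearly all of the bias, and the gap is under 1 h against an SE near 18 h.

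**Conclusion.** The point holds as a low-priority, inexpensive improvement to a supporting analysis. Both documents let the outcome data choose the adjustment set, by a bar that moves with the observed effect. That the bar scales with the estimate follows from the wording alone. How many covariates enter depends on the assumed R², independent covariates, normal errors and the chosen reading of the rule. The primary test, the sample size and the stated 79% power need no change.

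**What to change.** In Protocol 6.2 and SAP 1.2, delete the 10% rule and close the covariate list. Delete the imbalance clause there and in Protocol 6.3.1 and SAP 1.3.1. Keep the unadjusted intent-to-treat comparison as primary.

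Pre-specify one supporting linear model of total care time on arm plus age, gender, race, SES, Elixhauser index, treatment intent and performance status. All should be measured at or before randomization and retained whatever they do to the estimate. Report the adjusted difference in hours with its 95% CI.

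Before outcome data are seen, the sponsor should also fix:

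- **The coding, in few columns.** This covers the SES measure, the race grouping and the performance-status scale. The choice is the sponsor's.
- **A missing-covariate rule that ignores arm and outcome**, for example the column mean over both arms. Complete-case fitting would cost more than the covariates do. At an assumed 2% missing in each of the seven, 160 × 0.98⁷ ≈ 139 patients remain; at 5%, 160 × 0.95⁷ ≈ 112.

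The cost is a few sentences and these definitions. Section 3.3 of the protocol does not list the seven among the study measures. The planned baseline comparison implies that patient characteristics are collected, but the team should confirm each one. The statistical price is the loss of about 2 points (7 columns) or 3 points (12 columns) in the supporting model's power if the covariates predict nothing.

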6.3 Control of Bias and Confounding

Patients will be randomized 1:1 to control or intervention arm of the study. Despite the benefits of randomization to minimize the risks of confounding we will additionally perform a multivariate linear regression to adjust potential confounders including demographics as describe in section 6.2.

6.3.1 Baseline Data

Standard descriptive statistics will be calculated to compare patient characteristics for the intervention arm versus the control arm, such as medians and interquartile ranges for continuous variables and frequencies and proportions for categorical variables. These characteristics will be compared between the two groups using the Wilcoxon rank sum test for continuous variables and the chi squared or Fisher's exact test for categorical variables. We expect these characteristics will be similarly distributed between the intervention groups due to randomization, but in the case of imbalance, they may be adjusted in the multivariable model of the outcome.

6.3.2 Analysis of Primary Outcome of Interest

The primary analyses will be Intent-to-Treat, with the primary outcome (total care time measured over three months) compared using a two-sample t test, or Wilcoxon test if normal distribution assumption is violated (see section 6.2).

7 Safety and Adverse Events

7.1 Definitions

7.1.1 Adverse Event

An adverse event (AE) is any symptom, sign, illness or experience that develops or worsens in severity during the course of the study. Intercurrent illnesses or injuries should be regarded as adverse events. Abnormal results of diagnostic procedures are considered to be adverse events if the abnormality:

- results in study withdrawal
- is associated with a serious adverse event
- is associated with identification clinical signs or symptoms
 - This will be defined as immune related adverse events, per the NCCN guidelines regarding management of immune related adverse events⁴⁴, that result in treatment holds or steroid initiation.
 - Delayed identification of immune related adverse events, defined by symptoms or lab abnormalities that preceded a treatment infusion that was missed by e-triage or an office visit, will be documented separately.

CONFIDENTIAL

- leads to additional treatment or to further diagnostic tests
- is considered by the investigator to be of clinical significance

The objective of the pilot study is to optimize the questionnaire to quickly identify cancer related symptoms and immune related adverse events.

7.1.2 Serious Adverse Event

Serious Adverse Event

Adverse events are classified as serious or non-serious. A serious adverse event is any AE that is:

- fatal
- life-threatening
- requires or prolongs hospital stay
- results in persistent or significant disability or incapacity
- required intervention to prevent permanent impairment or damage
- an important medical event

Important medical events are those that may not be immediately life threatening, but are clearly of major clinical significance. They may jeopardize the subject, and may require intervention to prevent one of the other serious outcomes noted above. All adverse events that do not meet any of the criteria for serious will be regarded as non-serious adverse events.

7.2 Recording of Adverse Events

Trained research staff will be meeting with patients during each scheduled infusion visit. At each contact, they will seek information on adverse events by specific questioning and, as appropriate, by examination. Information on all adverse events will be recorded immediately in the source document, and also in the appropriate adverse event module of the case report form (CRF). All clearly related signs, symptoms, and abnormal diagnostic procedures results should be recorded in the source document, though should be grouped under one diagnosis.

All adverse events occurring during the study period will be recorded. The clinical course of each event will be followed until resolution, stabilization, or until it has been determined that the study intervention or participation is not the cause. Serious adverse events that are still ongoing at the end of the study period will be followed up to determine the final outcome. Any serious adverse event that occurs after the study period and is considered to be possibly related to the study intervention or study participation will be recorded and reported.

7.3 Relationship of AE to Study

Each adverse event to the study procedures will be characterized by the PI and classified as either definitely related, probably related, possibly related, unlikely, or unrelated based on documentation from the electronic medical record and as necessary discussions with the patient's medical provider.

7.4 Reporting of Adverse Events and Unanticipated Problems

The Investigator will promptly notify the Penn IRB of all on-site unanticipated, Adverse Events that are related to the research activity. Other unanticipated problems related to the research involving risk to subjects or others will also be reported promptly. Written reports will be filed using the HS-ERA and in accordance with the Penn IRB timeline of 10 working days.

7.4.1 Follow-up Report

If an AE has not resolved at the time of the initial report and new information arises that changes the investigator's assessment of the event, a follow-up report including all relevant new or reassessed

CONFIDENTIAL

information (e.g., concomitant medication, medical history) should be submitted to the IRB. The investigator is responsible for ensuring that all SAEs are followed until either resolved or stable.

7.4.2 Data and Safety Monitoring Plan

Overall data and safety will be monitored on an ongoing basis by the PIs and the study team. As needed, the investigators may decide to appoint an independent medical monitor to evaluate adverse events and make recommendations for continuing or stopping a trial. No interim analysis will be conducted.

Monitoring e-triage: All Waytohealth© interactions will be input into a flowsheet embedded into the patient's EMR and available to all study and clinical staff. All relevant persons will be notified via an EMR alert when any new information is entered. Dedicated research staff will be monitoring for inputs daily and will interphase with the research PI as well as clinical team as needed for unanticipated responses or symptoms. Any identified symptom will require the patient to have an in-person assessment with their routine clinical team. Clinical staff will be notified of the patient's triage status and offered the opportunity to mandate an in-person assessment regardless of the patient's triage status. A patient's enrollment in the study will be terminated if they experience an emergency medical situation requiring intervention or violate study protocol.

Monitoring clinical events: Research staff will see patients at each of their infusion visits. During this time, they will assess for any unidentified immunotherapy adverse events as well as screen for any emergency department visits or hospitalizations which occurred outside the Penn system. Additionally, research staff will receive EPIC alerts corresponding to any emergency department visits or hospitalizations.

8 Study Administration, Data Handling and Record Keeping

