Intervention	
Pilot study to optimize instrument performance:
 
 Prior to their scheduled immunotherapy infusion, consented patients will receive a text-based e-triage questionnaire. Following completion of the questionnaire, patients will proceed to their in-person assessment and providers will screen patients for potential immune related adverse events per routine care. Performance of the e-triage system will then be compared to the provider progress note documented in the EMR as the gold standard. 
Randomized control trial:
 
 Treatment arm: For patients in the intervention arm, symptoms and laboratory results will be assessed using the text-based e-triage 96 hours prior to their intended infusion date. The e-triage will consist of a standardized questionnaire and algorithm to evaluate symptoms and laboratory values. Patients with acceptable labs and minimal or no symptoms can opt to proceed directly to their immunotherapy infusion without an in-person office assessment. Usual Care: Patients in the usual care arm will receive standard of care symptom monitoring including an in-person office assessment prior to their scheduled immunotherapy infusion.

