3.3 Study Measures

AIM 1 Pilot study:

- **E-triage:** The e-triage will consist of 16 questions, modified from the validated NCI Pro-CTCAE™, which will be sent to patients via WaytoHealth®'s two-way texting system 96 hours prior to their scheduled immunotherapy infusion (see appendix B). Questions will pertain to common or emergent immune related adverse events as defined by the NCCN guidelines and two senior disease experts⁴²⁻⁴⁴. Patients will be prompted via text to measure the presence and severity of symptoms over the week prior. A final question will be included to capture any additional symptoms patients wish to disclose.
- **NCI Pro-CTCAE™:** A subset of patients may be asked to fill out a subset of the NCI PRO-CTCAE™, a set of validated questions for the collection of patient-reported outcomes to capture symptomatic adverse events in patients on cancer clinical trials, in order assess construct validity.
- **Definition of gold standard:** Patient reported toxicity captured by the text-based instrument will be compared to provider reported toxicity as documented in the EMR as the gold standard. To assess provider reported toxicity, standardized abstraction protocols will be developed by the PI and implemented by trained research staff.

AIM 2 Randomized control study:

- **Care time:** Care time will be defined as total time spent commuting to and receiving cancer care (including time spent obtaining labs). This will be captured using a combination of time-stamp information abstracted from AirFinder®, a real time patient located system deployed in the Perelman Cancer Clinics, and self-reported time for commuting and time spent obtaining local labs. Commute times will also be estimated using the patient's home address geocoded using ArcGIS software.
- **Emergency department and hospitalization rates:** Total number of emergency department visits and hospitalizations will be collected using data abstracted from the Penn electronic medical record during a 3 month follow-up window as well as through patient check-ins with study staff during routine infusion visits to account for care received outside the Penn system.

CONFIDENTIAL

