5.2 Study timeline

5.2.1 Pilot

During the pilot, consented patients will be enrolled onto the Waytohealth© texting system and sent the text-based e-triage 4 days prior to their infusion. They will otherwise participate per their usual oncology care, which includes an in-person office visit. Following this visit, trained research staff will abstract relevant clinical information related to treatment toxicity as documented in the progress note from the electronic medical record.

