10.3 Risk Benefit Assessment

Although there are potential risks associated with this study, the current model of cancer care delivery is inefficient resulting in long wait times and care delays, all of which is likely to worsen as the cancer population continues to grow. We have incorporated protocols to mitigate potential risks including integrating the e-triage into the EMR for easy access by clinician and research staff, the execution of a dedicated pilot study to ensure safety, and the fact the instrument is designed to prompt a formal clinical evaluation for any level of report toxicity. Additionally, the potential benefits of this study are great and

CONFIDENTIAL

include the ability to streamline care, improve access, and increase the patient-centeredness of cancer care delivery by allowing patients the option whether or not to see their provider if they are clinically well. If proven successful, this study could have a significant impact on oncology care across health systems.

10.4 *Informed Consent Process / HIPAA Authorization*

All subjects for this study will be provided a consent form describing this study providing sufficient information for subjects to make an informed decision about their participation in this study. See appendix D for a copy of the Subject Informed Consent Form. This consent form will be submitted with the protocol for review and approval by the IRB for the study. The formal consent of a subject, using the IRB-approved consent form, must be obtained before that subject undergoes any study procedure. The subject must sign the consent form, and the investigator-designated research professional obtaining the consent. Subjects will be consented by the study Principal Investigator, or appropriate designee, in a room we have selected in which to perform consent, which is located outside of the clinic. Potential subjects will review the consent form in detail with the person designated to consent (either PI or CRC) and have the ability to take the consent home for further review.

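### The pilot's reference standard is not protected from the e-triage answers: nothing keeps note authors or note abstractors unaware of them

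*Protocol*

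**What the plan says.** **Order of events.** Pilot patients are enrolled on the texting platform and "sent the text-based e-triage 4 days prior to their infusion" (Protocol 5.2.1). They then attend their usual office visit. The Study Summary gives the same order: questionnaire, provider assessment, comparison with the note.

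**Reference standard.** "Patient reported toxicity captured by the text-based instrument will be compared to provider reported toxicity as documented in the EMR as the gold standard" (Protocol 3.3). After the visit, "trained research staff will abstract relevant clinical information related to treatment toxicity as documented in the progress note" (5.2.1). Section 3.3 asks for standardized abstraction protocols and trained staff. It does not ask that abstractors be unaware of the answers.

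**Visibility of the answers.** Under Protocol 7.4.2 all WaytoHealth interactions "will be input into a flowsheet embedded into the patient's EMR and available to all study and clinical staff", and "All relevant persons will be notified via an EMR alert when any new information is entered". Dedicated research staff check the inputs daily. Section 10.3 lists among the risk safeguards "integrating the e-triage into the EMR for easy access by clinician and research staff". Neither section limits this to the randomized trial.

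**Interim result.** Protocol 6.1 and SAP 1.1 report 48 patients, documented toxicity in 53.2%, and sensitivity for at least one toxicity of 100% (95% CI 0.863 to 1.00). They project a half width of no more than 7% with 47 patients. A version 2 of the instrument was created after this look.

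**The concern.** A sensitivity estimate needs a reference standard formed without knowledge of the test result. Here the test comes first, its result sits in the record in which the reference standard is written, and no masking is described at either step:

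- A provider who has seen the answers may document a symptom that would otherwise have gone unrecorded, or may record nothing after a clean screen.
- An abstractor who has seen the answers may settle an ambiguous note in either direction. Section 7.4.2 has research staff reading the answers daily, and sections 3.3 and 5.2.1 have research staff abstracting the notes. Nothing separates the two tasks.

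All these effects favour the instrument. The stake is the pilot's main claim. Hypothesis H1 (Protocol 2.1) is 100% sensitivity, and sections 10.1 and 10.3 cite the pilot as a safeguard for a trial in which some patients go to infusion without an office visit.

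**Working it through.** **1. Reproduce the plan's figure.** The stated 53.2% fits 25/47 = 0.532. It does not fit 25/48 = 0.521 or 26/48 = 0.542, so the denominator appears to be 47 although the text says 48. For n out of n, the exact two-sided 95% lower limit is 0.025^(1/n). With n = 25 this is 0.025^(1/25) = 0.863, and the half width is (1 − 0.8628)/2 = 6.9%. Both published figures reproduce as 25/25.

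**2. Positive answer leads to documentation.** Let *a* be the documented toxicities that the screen caught and *b* those it missed. Prompting *k* extra entries changes *a*/(*a*+*b*) to (*a*+*k*)/(*a*+*b*+*k*). This is larger when *b* > 0 but still below 1. As a hypothetical case, 17/20 = 85% becomes 27/30 = 90%. With *b* = 0 the point estimate stays at 100% and only the interval changes. The documents give no value for *k*, so these are assumed values:

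| Prompted *k* of 25 | Unprompted | Exact lower limit | Half width |
|---|---|---|---|
| 0 | 25/25 | 0.863 | 6.9% |
| 1 | 24/24 | 0.858 | 7.1% |
| 5 | 20/20 | 0.832 | 8.4% |
| 10 | 15/15 | 0.782 | 10.9% |

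The 7% precision target is passed at the first prompted case.

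**3. Effect on specificity.** A prompted patient would otherwise have been a false positive. On the 25/47 reading, 47 − 25 = 22 patients have no documented toxicity. Without prompting there would be 22 + *k*, with the same number of true negatives. The observed specificity would then shrink by the factor 22/(22 + *k*): 0.957 for *k* = 1, 0.815 for *k* = 5, 0.688 for *k* = 10. Table 1 shows no specificity, so only the factor can be given.

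**4. Negative answer leads to omission.** If *m* toxicities were not documented or not abstracted because the screen was negative, the unbiased figure is 25/(25 + *m*), again with *m* assumed:

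- *m* = 1: 25/26 = 96.2% (exact 95% CI 0.804 to 0.999)
- *m* = 2: 25/27 = 92.6% (0.757 to 0.991)
- *m* = 3: 25/28 = 89.3% (0.718 to 0.977)

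Of the two routes, only this one can turn a sensitivity below 100% into 100%. Both together, with *k* = 5 and *m* = 2, give 20/22 = 90.9% (0.708 to 0.989).

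**5. Evidence within Table 1.** Pain 0.43 (0.10 to 0.82), rash 0.33 (0.01 to 0.91) and cough 0.50 (0.01 to 0.99) match 3/7, 1/3 and 1/2 with exact limits. The notes therefore held about 4 + 2 + 1 = 7 item-level entries that the e-triage did not report.

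**The case against.** **The monitoring paragraph may not describe the pilot.** Section 7.4.2 never names the pilot and does not list the treating provider among those alerted. Part of it fits only the randomized trial: "Clinical staff will be notified of the patient's triage status and offered the opportunity to mandate an in-person assessment" has no function when every patient is seen, and the statement that no interim analysis will be done cannot describe a pilot that reports one. The pilot text speaks only of usual or routine care. This stands as far as it goes. A reader might infer that pilot providers were alerted, and the documents do not establish that. They do not exclude it either: the wording covers all interactions, pilot patients are on the platform (5.2.1, 8.1), and section 7.1.1 states the pilot's objective within the same chapter.

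**The 100% is not explained by copying.** A reader might infer that providers copied the answers and so produced the 100%. Step 2 shows that copied positives cannot do this, and the roughly seven unmatched entries in Table 1 argue against wholesale copying. They do not rule out partial prompting, and they say nothing about omissions after a negative screen.

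**Sensitivity is not the only safeguard.** Skipping the visit also requires normal laboratory results and a complete questionnaire. Patients and providers can override, and vital signs and staff toxicity checks remain (5.2.2, 10.1). This is correct, and it limits the consequence. It does not make the sensitivity estimate independent of the test.

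**Conclusion.** The point holds as a gap in protection, not as a demonstrated bias. The reference standard follows the index test, the answers are described as visible to study and clinical staff with no pilot exemption, and neither the note author nor the abstractor is masked. The abstractor gap does not depend on whether the alert ran in the pilot, because research staff both monitor answers and abstract notes. The documents do not say whether the same individuals do both.

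The size cannot be determined. Under the assumed ranges, prompting 1 to 10 of the 25 positives lowers the exact limit from 0.863 to between 0.858 and 0.782 and leaves the estimate at 100%. One to three omissions after a negative screen would lower the estimate itself to between 96.2% and 89.3%. These figures rest on reading the interim result as 25/25 among 47 patients. The documents do not support saying that the reported 100% is false.

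**What to change.** 1. **Mask the abstractor.** For the remaining pilot patients (version 2), require that whoever abstracts a note has not seen that patient's e-triage answers, by dividing the tasks among existing staff. Re-abstract the interim notes the same way where feasible. This removes bias at abstraction but not any prompting of the note's author.
2. **State the facts.** Say in Protocol 3.3 or 5.2.1 whether the flowsheet and alert were active in the pilot, from when, and who could see them.
3. **If they were active,** use EMR access time stamps to report sensitivity and specificity by whether the note's author opened the answers before signing. Label this a descriptive sensitivity analysis. The unopened group may be small, and if opening depends on the answers it is selected on the test result, so it cannot serve as an unbiased estimate.

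Nothing is withheld from clinicians and care does not change. The costs are a small staffing constraint, some re-abstraction work, an audit-log query, and a wider interval in the subset.
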